#### Supplementary Estimands for primary endpoint:

##### Supplementary Estimand 1

Same components as the primary estimand, except for the strategy used for treatment discontinuation.

**Hypothetical strategy:** assess the treatment effect as if the participants would not have discontinued treatment.

Note: Under this hypothetical strategy, EASI data collected after treatment discontinuation will not be used and will be set to missing in analysis.

##### Supplementary Estimand 2

Same components as the primary estimand, except for the strategy used for treatment discontinuation.

**Treatment policy strategy:** assess the treatment effect regardless of treatment discontinuation.

Note: Under the treatment policy strategy, EASI data collected after treatment discontinuation will also be used in analysis.

### **5.3.3. Data Handling**

Participants who discontinued treatment prior to Week 16 will be considered EASI-75 non-responder at Week 16. In addition, participants with missing EASI evaluation at Week 16 will be considered as non-responders at Week 16.

### **5.3.4. Analysis Methods**

The primary endpoint will be compared between the each bermekimab group and the placebo group. The primary endpoint will be analyzed at Week 16 based on the composite estimand (Section 5.3.2) and the data from all participants in FAS (Section 2.4.1.1) will be analyzed according to randomized treatment group regardless of the treatment actually received.

In this primary analysis, the number and proportion of participants who achieve an EASI-75 at Week 16 will be summarized for each treatment group. To address the primary objective, a CMH chi-square statistic stratified by baseline EASI severity (less severe [EASI <28] or more severe [EASI ≥28]) at an alpha level of 0.05 will be used to compare each bermekimab group separately with placebo. The proportion difference between each bermekimab group and placebo group and its 2-sided 95% CI will be provided based on normal approximation with Mantel-Haenszel weights adjusting for baseline EASI severity.

### **5.3.5. Analysis for Supplementary Estimands**

#### **Supplementary Analysis 1 (Hypothetical Estimand)**

Under this estimand, for subjects who do not return for evaluation or discontinued study treatment for any reason, EASI score will be considered missing after discontinuation and missing data will be imputed using multiple imputations (MI) by fully conditional specification (FCS).

More specifically, the missing EASI-75 response will be imputed with FCS logistic regression including treatment group, baseline EASI, and EASI-75 response status through Week 16 in the model with seed = 789 and 500 imputations. The proportion difference of EASI-75 response at Week 16 adjusted for baseline EASI severity using Mantel-Haenszel weight between the bermekimab groups and the placebo group and its 95% CI combining multiple datasets will also be provided. In addition, the p-value for testing the treatment difference will be obtained from SAS PROC MIANALYZE based on these combined Mantel-Haenszel estimates from the multiple imputation datasets.

#### **Supplementary Analysis 2 (Treatment Policy Estimand)**

The primary endpoint will be analyzed utilizing the treatment policy estimand. For participants who do not return for evaluation or skipped visit at Week 16, the analysis will be performed using observed data regardless of treatment discontinuation. The EASI-75 values collected after treatment discontinuation will be used in analysis and missing data will not be imputed.

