### **5.3 DISCONTINUATION OF THERAPY**

If a patient is discontinued from study, the reason for discontinuation/withdrawal must be clearly documented in the source documentation and the EDC. Every effort should be made by the investigative site to have subjects who discontinue early from study complete all assessments included in the Early Termination visit included in the study calendar provided in section 5. All subjects will be unblinded after clinical database lock.

Study therapy **MUST** immediately be discontinued for any the following reasons:

- Withdrawal of informed consent (subject's decision to withdraw for any reason)
- Any clinical adverse event, laboratory abnormality, inter-current illness, or clinical progression of disease which, in the opinion of the Principal Investigator, indicates that continued participation in the study is not in the best interest of the subject
- Pregnancy
- Termination of the study by the sponsor
- Imprisonment or the compulsory detention for medical treatment.

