#### **2.4.1. Efficacy Analysis Set(s)**

##### **2.4.1.1. Full Analysis Set**

The full analysis set (FAS) population includes all randomized participants who received at least 1 dose of study agent. This analysis set will be used for the efficacy analyses of the endpoints through Week 36, *unless otherwise specified*.

In the efficacy analyses, participants will be analyzed according to the randomized treatment groups they were assigned to, regardless of the treatments they actually received.

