### **5.2.2. Data Handling Rules**

No imputation will be performed for missing baseline values.

For the main analysis of primary endpoint of EASI-75 response at Week 16, a subject who discontinued treatment will be considered as a non-responder from that point onward. The remaining missing data will be imputed as non-responder. Supplementary analyses will be performed and include (1) using observed data regardless of whether the subject discontinued treatment or have missing data, and (2) data after treatment discontinuation will be considered as missing, missing response will be imputed by multiple imputation methods under the assumption of missing at random. Similar data handling rules (i.e., main analysis with non-responder imputation and 2 supplementary analyses) will also be applied for EASI-75 response over time through Week 16. The following data handling rules will be applied for other endpoints:

Binary secondary endpoints:

- Analyses will be similar to the main analysis of the primary endpoint. A subject who discontinued treatment will be considered as a non-responder from that point onward. The remaining missing data will be imputed as non-responder. Supplementary analyses will be performed for selected endpoint (i.e IGA responses) in the same manner as the primary endpoint.

Continuous secondary endpoints:

- If a subject discontinued treatment, zero will be assigned to improvement or percent improvement. Remaining missing data will not be imputed. A MMRM model will adjust for missing post baseline data and all available data from the 3 treatment groups through Week 16 or from Week 16 through Week 36 will be included. Under the assumption of missing at random (MAR), the missing data will be accounted for through correlation of repeated measures in the model. Supplementary analyses will be performed for selected endpoints (i.e. EASI total score, NRS itch score) and include (1) using observed data regardless of whether the subject discontinued treatment or have missing data, and (2) data after treatment discontinuation will be considered as missing, missing data will be addressed by MMRM model.

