#### 5.3.2. Estimands

##### Primary Estimand:

The **Composite Estimand** will be targeted for the primary endpoint. The Composite Estimand for the primary endpoint is defined by the following 5 attributes:

- Treatment:
  - Bermekimab 400mg q2w
  - Bermekimab 400mg qw

- Placebo

Note: treatment regimen includes protocol specified rescue therapy as needed.

- Population: Adult participants with chronic moderate to severe atopic dermatitis present for at least 3 years.
- Variable (Endpoint): EASI-75 binary responder variable at Week 16, where a subject who discontinues treatment is considered as non-responder after discontinuation.
- Intercurrent event: The intercurrent event of treatment discontinuation is addressed by the composite strategy, as reflected in the variable definition.
- Population-level summary: Difference in the proportions of subjects achieving EASI-75 response at Week 16 between the bermekimab and placebo treatment groups.

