##### **5.4.4.2. Analyses Related to IGA**

- The proportion of subjects achieve an IGA score of clear (0), IGA score of clear (0) or almost clear (1), and IGA score of mild or better ( $\leq 2$ ) and at least 2 grade improvement from baseline at Week 16 will be compared between each of the bermekimab groups and the placebo group.
- The proportions of subjects who achieve an IGA score of clear (0) response, IGA score of clear (0) or almost clear (1) response, and IGA score of mild or better ( $\leq 2$ ) and at least 2 grade improvement from baseline response over time will be summarized by treatment group. In addition, supplementary analyses for the proportion of participants who achieve IGA responses through Week 16 will be performed utilizing the hypothetical estimand (i.e. MI method where appropriate using the similar method as for EASI-75) and treatment policy estimand (i.e. observed data).
- Line plots will be provided displaying the proportions and 95% CIs of subjects achieve an IGA score of clear (0); and an IGA score of clear (0) or almost clear (1) through Week 16 by treatment group.

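### Supplementary Analysis 2 is labelled treatment policy but uses observed cases only, so it matches its estimand only if Week 16 missingness is unrelated to response

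*SAP*

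**What the plan says.** SAP 5.3.2 sets up Supplementary Estimand 2. It keeps every component of the primary estimand except the strategy for treatment discontinuation, which becomes treatment policy: "assess the treatment effect regardless of treatment discontinuation". Efficacy is analysed in the FAS, which "includes all randomized participants who received at least 1 dose of study agent" (SAP 2.4.1.1). The primary estimand carries a note, inherited here, that "treatment regimen includes protocol specified rescue therapy as needed".

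The estimator is in SAP 5.3.5, Supplementary Analysis 2: "For participants who do not return for evaluation or skipped visit at Week 16, the analysis will be performed using observed data", and then "The EASI-75 values collected after treatment discontinuation will be used in analysis and missing data will not be imputed". SAP 5.2.2 gives the same rule in general form: "using observed data regardless of whether the subject discontinued treatment or have missing data". It is reused for EASI-75 through Week 16 (SAP 5.4.2.2) and for IGA (SAP 5.4.4.2), where the shorthand is "treatment policy estimand (i.e. observed data".

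The other two analyses of the primary endpoint do say what happens to missing data. The main analysis counts a missing Week 16 EASI as non-response (SAP 5.3.3). Supplementary Analysis 1 uses multiple imputation by fully conditional specification (SAP 5.3.5).

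On data collection, Protocol 5.3 asks sites to make every effort to "have subjects who discontinue early from study complete all assessments included in the Early Termination visit". SAP 2.2 assigns data to nominal visits, and no rule maps an Early Termination EASI to Week 16. The only explicit instruction to continue evaluations off drug is for participants unblinded by the investigator (SAP 1.5.2).

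**The concern.** A treatment policy estimand asks what happens at Week 16 in everyone in the analysis population, on or off drug. The analysis as written answers that only for patients who have a Week 16 EASI. Membership of that group is decided after randomisation and may depend on how the patient was doing, so the arms being compared need no longer be the randomised arms.

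The natural use of this analysis is to sit beside the primary result and show what changes when discontinuation is handled differently. If patients without data drop out of the denominator, both agreement and disagreement with the primary result become hard to read. The Week 16 results are also meant to inform planning of later development (SAP 2.4), where an effect size described as treatment policy may be taken at face value.

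**Working it through.** **Inputs.** Planned response is 60% in Arm 1 (weekly) and 20% in Arm 3 (placebo). The requirement is 23 per arm at two-sided 0.05 with about 80% power, and about 90 patients are randomised 1:1:1, so 30 per arm (Protocol 10.1, SAP 1.4). The documents give no dropout rate; every missingness rate below is an assumption. One of them, 7/30 = 23.3%, is the gap between 30 and 23 per arm. The plan gives that excess two purposes, dropouts and safety data, so it is not a planned dropout rate.

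**1. The plan's own figure.** With pooled variance under the null, n = [1.96 × √(2 × 0.4 × 0.6) + 0.842 × √(0.24 + 0.16)]² / 0.4² = 22.3, so 23 per arm. Power at 23 is 81.2%. The stated sample size reproduces and is not in question.

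**2. When the estimator hits the estimand.** In an arm with missing fraction m, response p_obs among those observed and p_mis among those missing, the full-cohort rate is (1 − m) × p_obs + m × p_mis. The observed-case error in that arm is therefore m × (p_obs − p_mis). The error in the difference is the active-arm term minus the placebo-arm term. Apart from chance cancellation, it is zero only if p_obs = p_mis in each arm. Its sign is not fixed.

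**3. Size if every missing patient is a non-responder.** Then p_mis = 0 and the observed rate is the full-cohort rate divided by (1 − m). The full-cohort difference is 60% − 20% = 40.0 points.

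| Missing, active / placebo (assumed) | Observed rates | Difference (points) | Change |
|---|---|---|---|
| 10% / 10% | 66.7% / 22.2% | 44.4 | +4.4 |
| 23.3% / 23.3% | 78.3% / 26.1% | 52.2 | +12.2 |
| 30% / 10% | 85.7% / 22.2% | 63.5 | +23.5 |
| 10% / 30% | 66.7% / 28.6% | 38.1 | −1.9 |
| 10% / 40% | 66.7% / 33.3% | 33.3 | −6.7 |

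**4. Range without that premise.** Take 30 per arm, 18 and 6 observed responders, and 7 missing in each arm. The lowest possible full-cohort difference is 18/30 − 13/30 = 16.7 points; the highest is 25/30 − 6/30 = 63.3 points. The observed-case figure is 18/23 − 6/23 = 52.2 points, one value within a wide range.

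**5. Can the reading change?** Yes, in both directions (30 per arm, unstratified chi-square, illustrative counts):
- 11 versus 5 responders with 7 active and 3 placebo missing: counting missing as non-response gives 20.0 points, p = 0.080; observed cases give 11/23 − 5/27 = 29.3 points, p = 0.027.
- 12 versus 5 responders with 3 active and 7 placebo missing: non-response gives 23.3 points, p = 0.045; observed cases give 12/27 − 5/23 = 22.7 points, p = 0.091.

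**The case against.** The best defence is that the SAP is open about the method. It says observed data in three places, keeps off-treatment values where they exist, and offers this as one of two supplementary analyses behind a main analysis that handles missing data conservatively. Success is judged on the primary comparison (SAP 5.2.1). All of that stands and limits what is at stake. It does not cure the mismatch, because the treatment policy label stays attached to an estimator that needs an unstated assumption.

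A reader might infer more than the documents support:

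- *That this is a completer analysis dropping everyone who stops drug.* It is not. A patient who stopped treatment but has a Week 16 EASI is included. Even the exclusion of those without one is inferred from the no-imputation wording, since the SAP never states the denominator.
- *That few off-treatment Week 16 values will exist.* Protocol 5.3 asks for an Early Termination visit from patients who leave the study. It is silent on whether those who only stop drug keep their scheduled visits. The protocol is unclear here; it does not rule such data out.
- *That the analysis will flatter the drug.* The 10%/30% and 10%/40% rows shrink the effect.
- *That the 40-point benchmark is the treatment policy truth.* It is so only if every missing patient is a non-responder. The SAP's estimand counts rescue as part of the regimen, so a patient with no Week 16 EASI could be a responder.

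**Conclusion.** The mismatch is real and lies in a stated rule, not in missing detail. Supplementary Analysis 2 is an observed-case analysis under a treatment policy label, and it recovers the stated estimand only if Week 16 missingness is unrelated to response within arm.

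Under the assumed rates, and if missing patients are all non-responders, 40 points becomes anything from about 33 to about 63. Neither the rates nor that premise comes from the documents, so these figures show sensitivity and do not predict bias. The primary non-responder analysis, the sample size and the success rule do not change. The harm is a mislabelled supplementary result that may reassure or alarm for the wrong reason.

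**What to change.** In SAP 5.3.5, and in the matching sentence of 5.2.2:

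1. State that the denominator is all FAS patients.
2. Use every Week 16 EASI collected after treatment discontinuation.
3. Multiply impute the remaining missing values under a stated off-treatment or reference-based assumption. The imputation already specified for Supplementary Analysis 1 can be adapted, but it sets post-discontinuation data to missing and targets the hypothetical estimand, so it cannot be reused unchanged.
4. Add a tipping-point check that varies response among the imputed patients in each arm separately.
5. Do not fill all gaps with non-response, since that largely repeats the primary composite analysis.
6. Apply the same rule to EASI-75 over time (5.4.2.2) and IGA (5.4.4.2). Keep the present version, if wanted, under the label *observed cases*.

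The protocol should also make clear that patients who stop drug but remain in the study still have the scheduled Week 16 EASI.

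Cost: one more imputation specification, a clarification to sites, and the effort of obtaining that visit from patients off drug. The visit and assessment are already in the study calendar. The result will rest on an imputation assumption, and more heavily so if off-treatment data prove sparse, but the assumption will be stated and tested.

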### **5.3.6. Subgroup Analysis**

For each of the subgroups defined in Section 2.5, the difference between each of the bermekimab treatment group and placebo group in the proportion of participants achieving EASI-75 at Week 16 and its 95% confidence interval (when the number of participants permits) will be calculated. Subgroup analyses will not be stratified by baseline EASI severity.

In addition, the proportion of participants achieving EASI-75 at Week 16 by investigator site will be summarized. The same data handling rules specified in Section 5.2.2 will apply for subgroup analysis.

### **5.3.7. Per-protocol Analysis**

The primary estimand will also be performed on per-protocol analysis set (Section 2.4.1.2). The same data handling rules specified in Section 5.3.3 will apply.

## **5.4. Secondary Efficacy Endpoints**

This section outlines the definition and analyses of these secondary endpoints related to NRS, EASI, IGA, DLQI, HADS, POEM, SCORAD, and GISS. Data from all participants in FAS will be included and analyzed according to the randomized treatment groups. For participants randomized to placebo, only participants who crossed over to receive bermekimab at Week 16 will be included in the efficacy summaries for the visits after Week 16. All statistical testing will be performed at the 2-sided 0.05 significance level. Nominal p-values will be presented.

Secondary efficacy endpoints will be summarized using descriptive statistics for continuous variables (n, mean, standard deviation, median, minimum and maximum value) and number and percentage for categorical variables. Continuous endpoints will be analyzed using a MMRM model to test the difference between treatment groups and adjust for missing data. The MMRM will include treatment, visit, baseline EASI severity, baseline score, baseline score by visit interaction, baseline EASI severity by visit interaction and the treatment-by-visit interaction, if applicable. The Least Square mean (LSmean) estimates and their corresponding 95% confidence interval (CI) will be provided at each time points. In addition, the estimates of LSmean difference and 95% CIs between treatment groups will be provided over time through Week 16 and p-values will be calculated at Week 16.

For the MMRM model, an unstructured covariance matrix for repeated measure within a participant will be used. In case that convergence cannot be achieved, autoregressive (1) covariance structure will be used.

For binary response endpoints, treatment comparisons will be performed using a Cochran-Mantel-Haenszel (CMH) test stratified by baseline EASI severity with missing data imputed with Non-Responder Imputation (NRI) defined in Section 5.2.2. In case of rare events, the Fisher's Exact test will be used for treatment comparisons in binary response endpoints.

Graphical data displays may also be used to summarize the over time data if applicable.

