### **5.4.3. Numerical Rating Scale (NRS) for Itch & Pain**

#### **5.4.3.1. Definition**

Patients will be given a diary to complete each night before bed. Patients will be asked to report “average pain”, and “worst moment pain” as well as “average itch” and “worst moment itch” on a 0-10 numeric rating scale. Patient diaries will be collected weekly. A higher score indicates more severe disease (0 indicate no itch or no pain). The baseline is defined as the average score of last 7 days prior to Week 0 study agent administration. If there are more than 3 days missing data, then baseline is set as missing. Missing baseline will not be imputed.

Seven daily NRS scores are averaged into a weekly score (ie 7 days [from day -7 to -1] prior to a visit). Four days out of 7 days (either consecutive or nonconsecutive) are necessary to derive a weekly score; otherwise data are considered missing for that week.

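### If the unstructured MMRM fails to converge, the SAP's only fallback is AR(1), which can understate the Week 16 standard error of the continuous secondary endpoints

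*SAP*

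**What the plan says.** SAP 5.4 sets the first choice: "For the MMRM model, an unstructured covariance matrix for repeated measure within a participant will be used". The next sentence is the whole contingency: "In case that convergence cannot be achieved, autoregressive (1) covariance structure will be used". The SAP names no intermediate structure, robust standard error or degrees-of-freedom method. Protocol 10.5.3.2 specifies REML and the fixed effects but no covariance.

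The same SAP section states "All statistical testing will be performed at the 2-sided 0.05 significance level" and "Nominal p-values will be presented". For the MMRM comparisons, "p-values will be calculated at Week 16", although differences and intervals are shown at earlier visits too. On the data entering the model, SAP 5.2.2 says "all available data from the 3 treatment groups through Week 16 or from Week 16 through Week 36 will be included".

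For itch and pain, SAP 5.4.3.1 says "Seven daily NRS scores are averaged into a weekly score", so up to 16 post-baseline values per patient exist through Week 16. The SAP does not list which of them enter the NRS model. EASI and the other clinic scores are taken at Weeks 1, 2, 4, 6, 8, 12 and 16 (Protocol 5.2.1).

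**The concern.** AR(1) in its usual form has two parameters: one variance for all visits and one correlation per visit step. If patients' scores diverge over time, that single variance averages small early values with larger late ones. It is then too small for the last visit, which is the one tested. On the clinic schedule AR(1) also treats a one-week gap and a four-week gap as the same step; that second point does not apply to equally spaced weekly NRS scores.

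At stake are the Week 16 intervals and nominal p-values for the MMRM endpoints: EASI improvement, continuous itch and pain, DLQI, HADS, POEM, SCORAD, BSA and GISS. SAP 2.4 puts EASI and the NRS scores into the Week 16 lock, which is meant to inform further development. Intervals that are too narrow there could make an effect look better established than it is. A replacement structure is also hard to choose neutrally once sponsor staff are unblinded at that lock.

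**Working it through.** **The plan's own figure.** The only design calculation is for the primary endpoint. With 60% vs 20%, two-sided 0.05 and 80% power, n = [1.96·√(2·0.4·0.6) + 0.8416·√(0.6·0.4 + 0.2·0.8)]² / 0.4² = 22.3, so 23 per group, with power 81.2%. It reproduces. It says nothing about the MMRM, for which the documents give no SD, correlation or dropout rate.

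**Inputs.** About 90 patients, 1:1:1 (SAP 1.4, 1.5.1); two-sided 0.05 (SAP 5.4). Assumed: SD rising linearly in calendar weeks from 1 at Week 1 to r at Week 16.

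**Closed form.** Treatment, severity stratum and baseline score are all crossed with visit. With complete data the Week 16 estimate is therefore the same under any covariance, and only its standard error changes. Taking the AR(1) variance as the average of the visit variances:

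- SE ratio q = √(mean of SD² over visits) / r
- actual error = 2·[1 − Φ(1.96·q)]

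With u = (week − 1)/15, mean SD² = 1 + 2(r−1)·mean(u) + (r−1)²·mean(u²).

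- 16 weekly visits: mean u = 0.5, mean u² = 0.3444. For r = 1.5, mean SD² = 1 + 0.5 + 0.0861 = 1.586; q = √(1.586/2.25) = 0.840; error 10.0%.
- Weeks 1, 2, 4, 6, 8, 12, 16: mean u = 0.4, mean u² = 0.2730. For r = 1.5, mean SD² = 1 + 0.4 + 0.0683 = 1.468; q = √(1.468/2.25) = 0.808; error 11.3%.

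| SD path to Week 16 | 16 weekly visits: q, error | Seven clinic visits: q, error |
|---|---|---|
| falls to 0.8 | 1.13, 2.7% | 1.15, 2.4% |
| constant | 1.00, 5.0% | 1.00, 5.0% |
| rises to 1.25 | 0.90, 7.7% | 0.88, 8.4% |
| rises to 1.5 | 0.84, 10.0% | 0.81, 11.3% |
| rises to 2 | 0.77, 13.3% | 0.72, 15.8% |
| same rises, level from Week 4 | 0.98 / 0.96 / 0.95; 5.6% / 5.9% / 6.3% | 0.96 / 0.93 / 0.90; 6.1% / 6.8% / 7.7% |

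The plain average is an approximation. AR(1) actually fits s² = trace(R⁻¹Σ)/T, with ρ minimising T·log s² + log|R|, where Σ is the true covariance, R the AR(1) correlation matrix and T the number of visits. For an assumed true correlation of 0.4 + 0.6·0.9^lag (lag in weeks), this gives 9.8% (weekly) and 10.5% (seven visits) at r = 1.5, and 12.7% and 14.1% at r = 2. These are slightly lower and lead to the same conclusion.

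**Simulation.** REML, 90 patients, the SAP's fixed effects, the same correlation, 5% intermittent missing:

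- AR(1), 20% dropout left missing: weekly, r = 1.5, SE ratio 0.855 and error 8.7% (400 runs); seven visits, r = 1.5, 0.785 and 13.0% (400 runs); seven visits, r = 2, 0.70 and 16.0% (400 runs); weekly, constant SD, 1.06 and 5.3% (300 runs).
- Unstructured, weekly, r = 1.5, 20% dropout left missing: 1.00 and 4.2% (120 runs).
- Weekly, r = 1.5, with 20% dropout set to zero improvement as in SAP 5.2.2: AR(1) 0.89 and 6.2%; unstructured 1.02 and 3.7% (80 runs).

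**Would the fallback be triggered?** An unstructured matrix needs T(T+1)/2 parameters: 136 for 16 visits, 28 for seven, 10 for four. With 16 visits it converged in 120 of 120 runs with 20% dropout left missing, 80 of 80 with dropout set to zero, and 60 of 60 with constant SD. In a stress case (35% dropout left missing, 10% intermittent missing) it converged in 59% of 80 runs within 50 iterations.

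Runs of 60 to 120 give rough error rates, and the fitting algorithm (Fisher scoring) may behave differently from the trial software.

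**The case against.** The case against is substantial, and most of it stands.

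- **Use of the fallback.** A reader might infer from 136 parameters and about 90 patients that AR(1) is likely to be used for NRS. The documents do not support that. They do not say that all 16 weeks are modelled, and the unstructured model converged in every run with moderate missingness. SAP 5.2.2 assigns zero improvement after treatment discontinuation, so those records are present in the main analysis. Heavy missingness is more plausible in the supplementary itch analysis of SAP 5.4.3.2, where data after discontinuation are set to missing.
- **Which endpoints.** A reader might also infer that the protocol's itch and pain endpoints are affected. They are binary (at least a 4-point improvement) and tested by CMH. Only the SAP's additional continuous NRS analyses use the MMRM.
- **The SD path.** Rising SD is an assumption. The earlier open-label study reports a 4-point improvement in overall itch in 61% of high-dose patients at Week 4 and 75% at Week 8 (Protocol 1.1), so an early plateau cannot be excluded. EASI-75 in the same study went from 39% to 75% between those weeks, so neither can a later rise. Both are response rates, not SDs.
- **The setting where it fails.** In the stress case AR(1) itself showed 5.0% error and an SE ratio of 0.97. With 80 runs this is too imprecise to show that AR(1) is safe there, but it gives no support for inflation either.
- **Importance.** The p-values are nominal, in a Phase 2 trial that accepts 0.10 overall error for its primary endpoint (SAP 5.2.1).

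What survives is narrower: a pre-specified fallback should be valid if triggered, and this one is valid only if variability does not grow.

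**Conclusion.** The point holds conditionally and has low priority. If the unstructured model fails, if AR(1) is read as homogeneous (the SAP does not use that word), and if residual SD rises steadily to Week 16, the model standard error there is about 10% to 28% too small for a 1.25- to 2-fold rise. Nominal 5% tests then run at roughly 8% to 16%. With constant SD there is no inflation, with an early plateau it is small, and with falling SD the analysis is conservative. Where SD rises, intervals at the earliest visits would err the other way, too wide.

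None of this shows that the reported Week 16 results will be too optimistic. That would need evidence on the SD path and on convergence that neither document contains. The primary analysis, the sample size and all CMH-tested endpoints are untouched.

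**What to change.** Replace the AR(1) sentence in SAP 5.4 with an ordered fallback that keeps a separate variance at each visit: heterogeneous Toeplitz, then heterogeneous AR(1) or heterogeneous compound symmetry. For 16 visits these need 16 + 15 = 31 and 16 + 1 = 17 covariance parameters, against 136 for unstructured. Whenever a structured covariance is used, base inference on sandwich standard errors with a small-sample correction; without one they can themselves be too small at about 30 patients per arm. Name the degrees-of-freedom method and list the visits in each MMRM.

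The cost is one or two SAP sentences, no new data, and slightly wider Week 16 intervals if the fallback is triggered. The change should be made before unblinding.

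Fitting the NRS model only at Weeks 4, 8, 12 and 16 would cut the unstructured matrix to 10 parameters and make failure improbable. This is optional, because it discards weekly values that SAP 5.2.2 says will be included.
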